4.3.2 Inclusion Criteria

Each infant must meet all inclusion criteria to be eligible for enrolment on this study:

1. Born between 22+0 and 31+6 weeks' gestation.
2. Birth admission in a participating perinatal Victorian NICU.
3. The infant has a parent/legal representative capable of understanding the informed consent document and providing consent on the infant's behalf AND consent is obtained antenatally or within 72 hours from birth.

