BPD status during 36 weeks' PMA will be assessed using the Modified Walsh definition and standard oxygen reduction test (ORT), and Jensen criteria for Grading from no BPD, mild, moderate and severe (Grade 0-3) (5, 10). Death before 36 weeks' PMA due to a primary respiratory cause will be coded as severe BPD using the 2018 NICHD Grade 3A BPD definition; *'early death between 14 days postnatal age and 36 weeks' PMA from persistent parenchymal lung disease and respiratory failure that is not attributable to other neonatal morbidities'*. Inclusion of death due to non-respiratory causes may result in misclassification in the prediction models. The primary and critical contributors to all deaths before 36 weeks' PMA will be documented to allow secondary analysis for 'all cause' mortality in the prediction models. The 36-week BPD Assessment should occur on the date determined to be 36+0 to 36+6 weeks PMA.

If the BPD assessment is completed outside of the 36+0 to 36+6 weeks' PMA assessment window, as the infant was discharged home from hospital early self-ventilating in air (SVIA) before 36+0 weeks PMA, then these infants will be coded as not having BPD. Should the condition of the infant change within the 36-weeks PMA (e.g. they are re-admitted to any hospital between discharge home and 36+6 weeks PMA), then the participating site must update the 36-Week PMA BPD Assessment CRF, if applicable.

Lung imaging will be repeated as per Section 6.2.4, and the appropriateness of studying the infant will be re-affirmed with the clinical staff. For scheduled weekly or pre-discharge measures, consent will also be re-affirmed with the parents/legal representative and documented in the participant's medical record as per the Manual of Operating Procedures.

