11 STATISTICAL METHODS

11.1 Sample Size Estimation

The sample size for BLUEPRINT is designed to address the robustness of early respiratory phenotypes identified predicting BPD. The prevalence of survival with BPD within the ANZNN is 0.69. Based on the R package *pmsampsize* version 1.1.3 described by Riley et al in “*Calculating the sample size required for developing a clinical prediction model*”,⁽³⁶⁾ we estimated that the following sample size will be required to develop a clinical risk prediction model with BPD (yes/no) as the outcome: assuming a BPD prevalence of 0.69 (69%; all grades) and a moderate C-index of 0.75 is achievable (latest estimates from PRELIM manuscript support this) with a binary logistic regression prediction model with BPD (yes/no) as the outcome, a minimum sample size of 500, 550 and 600 infants was estimated based on 10, 11 or 12 predictor variables respectively (from any domain of clinical, imaging and protein data). We estimate that the predictive model developed in BLUEPRINT may have up to 10-12 predictor variables which is partly based on the latest PRELIM manuscript where several basic clinical covariates (e.g. gender, gestational age) and only single proteins were included (given the limited sample size in PRELIM), however there were multiple proteins that were significantly correlated with BPD and there will be additional clinical covariates and other model terms (interactions, non-linear terms, which are counted as additional predictor variables terms in the *pmsampsize* sample size estimation) that will likely be critical to include in the BLUEPRINT study in order to achieve high performing predictive models.

The calculation above derived from the *pmsampsize* R package considers multiple criteria to arrive at an appropriate sample size that ensures precise predictions, minimises prediction errors and model overfitting/optimism, and allows for sufficient stratification by factors known to exert a strong signal on neonatal outcomes (e.g. gestational age/weight, sex and intubation in first 10 days).

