Development of a biomarker-based BPD risk (and 1 and 2 year) prediction model: We will develop a risk prediction model for BPD diagnosed at 36 weeks, based on a combination of proteins, imaging and clinical measures (minimum 7 inputs) derived within the first 7 days after birth. Model development will include several steps starting with methods for variable selection and model fitting to testing the performance and validation of models. To test measures originally significantly associated with BPD, and identify other measures that are predictive of BPD, binary logistic regression, multiple forward stepwise logistic regression, and other classification models will be evaluated with likely measures as covariates. This approach is similar to other recent studies that developed prognostic, biomarker-based models for predicting adverse outcomes in adults with respiratory problems. (34) Model performance and discrimination will then be evaluated. Internal validation with both cross-validation and bootstrapping methods to adjust for model over-optimism and bias towards inherent overestimated performance metrics will be applied. A similar strategy will be used for developing and testing risk prediction models at 1 and 2 years, which will include initial variable selection and subsequent model performance (AUC, discrimination) and validation (cross-validation) tests. We will examine several methods (e.g. growth curve trajectory) for coding repeatedly measured predictor variables that best capture developmental changes related to lung injury over time and subsequent respiratory risks. Cox proportional-hazards regression models and Kaplan-Meier survival curves will be used to further investigate and illustrate differences in BPD risk outcomes between high-risk and low-risk groups based on prognostic scores derived from BPD risk models, which will be useful to account for infants that may be lost to follow-up before 2 years.

Testing and developing alternative machine learning models of BPD risk.

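### Cox and Kaplan-Meier methods are planned for BPD, a status read once at 36 weeks: loss after 36 weeks cannot censor it, and on a clock from birth the high-risk group can appear protected

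*Protocol*

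**What the plan says.** Protocol section 11.2 first sets the target of the score: "We will develop a risk prediction model for BPD diagnosed at 36 weeks". Section 11.1 sizes the study for a "binary logistic regression prediction model with BPD (yes/no) as the outcome". Later in the same paragraph of 11.2 comes the sentence at issue: "Cox proportional-hazards regression models and Kaplan-Meier survival curves will be used to further investigate and illustrate differences in BPD risk outcomes". The groups compared are high-risk and low-risk infants according to the BPD score, and the stated benefit is "which will be useful to account for infants that may be lost to follow-up before 2 years".

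Section 6.2.7 fixes when BPD is read: "The 36-week BPD Assessment should occur on the date determined to be 36+0 to 36+6 weeks PMA". Infants who go home in air before 36+0 weeks are not dated either: "then these infants will be coded as not having BPD". There is one exception: "Death before 36 weeks' PMA due to a primary respiratory cause will be coded as severe BPD". Those deaths have dates of their own.

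Section 11.1 assumes 5% loss or withdrawal between the first week and the BPD assessment. The protocol gives no time origin, event date or censoring rule for the Cox and Kaplan-Meier analysis.

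**The concern.** Survival methods need an event that happens at a time, and censoring that hides whether or when it happened. BPD as defined here offers almost none of that. Its date is set by the calendar of the assessment, not by the disease. An infant seen at 36 weeks and lost at 14 months has a known BPD status, so the reason given for the method does not apply to this outcome. Only the assumed 5% lost before assessment is relevant.

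What is at stake is the display of the risk score. Objective 3 wants a tool for routine clinical use. If the curves are drawn from birth, the time axis mostly shows how early the infant was born. Gestational age is likely to be part of the score: section 11.1 names it among the covariates of the pilot model, section 2.1 lists gestation as associated with BPD, and section 9.2 calls it a major determinant of respiratory status. The infants scored as highest risk would then tend to have the longest time to BPD, and the hazard ratio could point away from the true risk.

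**Working it through.** **1. Design values.** The protocol states no figure for the Cox or Kaplan-Meier analysis, so the only figure to reproduce is the sample size that uses the same prevalence and C-index. With prevalence 0.69 and C = 0.75 the Cox-Snell R² is about 0.161. With shrinkage S = 0.9, n = P / [(S − 1) ln(1 − R²/S)] = P / [−0.1 × ln(0.821)] = P / 0.0197. For P = 10, 11 and 12 this gives about 507, 558 and 609, against the stated 500, 550 and 600 (within 2%). The design values are therefore sound inputs for what follows.

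**2. Time to BPD counted from birth.** The inclusion criterion is "Born between 22+0 and 31+6 weeks' gestation".
- Born at 22+0: 36w0d − 22w0d = 14w0d.
- Born at 31+6: 36w0d − 31w6d = 4w1d.

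The assessment window adds at most 6 days. When the infant born at 31+6 is recorded as having BPD at about 4 weeks, an infant born at 22+0 is in the risk set but cannot be diagnosed for roughly another 10 weeks. Immature infants thus add time at risk to every early event without being able to have one.

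**3. Time counted in PMA.** All assessed events tie at 36 weeks with everyone at risk. The Cox score equation (Breslow ties) is d₁ = d·n₁e^β / (n₀ + n₁e^β). Its solution is e^β = (d₁/n₁)/(d₀/n₀), the plain risk ratio. With 0.84 and 0.54 that is 0.84/0.54 = 1.56.

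**4. Size of the effect.** Simulation: 525 infants (the protocol's modelling set), 300 runs per setting, medians shown, score split at its median.
- From the protocol: prevalence 0.69, C about 0.75, 37% born before 28 weeks.
- Assumed: shares of 17%, 30% and 53% in the bands 22 to 25+6, 26 to 28+6 and 29 to 31+6 weeks, uniform within each (17% + 2/3 × 30% = 37% below 28 weeks); and the strength of gestational age in the score, with other predictors scaled to keep C near 0.75.

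| Gestational-age slope (logit/week, assumed) | True risk, low / high | HR, birth clock, non-BPD censored at assessment | HR, birth clock, non-BPD censored at 2 years | HR, PMA clock |
|---|---|---|---|---|
| 0 | 0.54 / 0.84 | 1.55 | 2.11 | 1.55 |
| 0.10 | 0.54 / 0.84 | 1.06 | 1.90 | 1.56 |
| 0.20 | 0.54 / 0.84 | 0.65 | 1.68 | 1.56 |
| 0.35 | 0.54 / 0.84 | 0.21 | 1.43 | 1.58 |
| 0.45 (score is gestational age alone) | 0.53 / 0.86 | near 0 | 1.34 | 1.60 |

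The true odds ratio is about 4.4 to 5.2 throughout. On the birth clock with censoring at assessment, the HR is below 1 in every run at slopes of 0.20 and above, in 29% of runs at 0.10, and in none at 0.

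**5. Curves when infants without BPD are censored at 2 years.** The HR stays above 1, but at 0.35 logit per week the Kaplan-Meier BPD incidence at 8 weeks is 0.50 in the low-risk half and 0.26 in the high-risk half. The early part of the plot still shows the wrong order.

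**6. Sensitivity.**
- Dating an assumed 2% of infants as respiratory deaths before 36 weeks moves the birth-clock HR from 0.65 to 0.69 (slope 0.20) and from 0.21 to 0.24 (slope 0.35).
- At assumed prevalences of 0.50 and 0.40, the HR is 0.86 and 1.00 at slope 0.20, and 0.26 and 0.29 at slope 0.35.

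**The case against.** The strongest reply is that the sentence means something else. The paragraph's title also covers the 1- and 2-year models, and the sentence follows text on those models and speaks of loss before 2 years. The authors may have meant the BPD score to define groups that are then followed for later respiratory events, in line with objectives 7 and 8. That reading is possible. But the sentence says BPD risk outcomes and names no dated event, so the wording needs correcting on either reading.

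A second reply is that clock and censoring rule can be left to the statistical analysis plan. This stands in part: no single hazard ratio can be attributed to the protocol. No such rule gives an onset time to a status read once, however, and the follow-up rationale is already written into the protocol.

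A reader might also infer more than the document supports:
- **That the hazard ratio will be reversed.** It depends on the clock, the censoring rule and the weight of gestational age. It does not happen on the PMA clock or with censoring at 2 years.
- **That BPD has no event time at all.** Respiratory deaths before 36 weeks coded as severe BPD are dated, although they change little.
- **That loss to follow-up is irrelevant.** The assumed 5% lost before assessment does matter.
- **That the main results are at risk.** The sentence offers further investigation and illustration. The primary outcome is the endotypes, the main BPD model is logistic, and the sample size rests on that model.

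**Conclusion.** The concern holds in a limited form. For 36-week BPD, Cox and Kaplan-Meier methods are the wrong tools, and loss between 36 weeks and 2 years is not a reason to use them. That follows from the protocol's own definitions and needs no simulation.

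How misleading the result would be depends on choices the protocol does not state. On a birth clock with censoring at assessment, the hazard ratio for high versus low risk runs from about 1.6 down to about 0.2 as the assumed slope rises from 0 to 0.35 logit per week, and approaches 0 if the score is gestational age alone. The true risks stay at about 0.84 and 0.54. With censoring at 2 years it is about 1.3 to 2.1, with early curves that can mislead. On the PMA clock it only repeats the risk ratio of about 1.6. Severity is moderate: a secondary display of the score is affected, while the logistic model and the sample size are not.

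**What to change.** In section 11.2, and in the statistical analysis plan to match:

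1. Remove Cox regression and Kaplan-Meier curves for BPD at 36 weeks. Report the observed BPD proportion with 95% CI in each predicted-risk group, and the risk difference or risk ratio between groups. State how non-respiratory deaths before 36 weeks are counted.
2. Treat infants lost before the BPD assessment (assumed 5%) as having a missing outcome, under the rules planned in section 11.3.
3. If the 2-year wording was meant for later respiratory outcomes, name the dated outcome, its time origin and its censoring rule, and treat death as a competing event.

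Items 1 and 2 cost only wording. Item 3 needs a check first. Section 6.2.9 collects respiratory events and admissions since the last assessment, and mortality before 1 year and at 2 years, without specifying dates. Dates of death are specified for the hospital stay only (sections 6.2.3, 6.2.6 and 6.2.8). The sponsor should confirm that the follow-up forms record event dates before committing to a time-to-event analysis.

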While binary logistic regression is commonly used for developing risk prediction models when disease outcomes are binary yes/no, it will be important to test alternative risk prediction models that may be better able to handle high dimensional data (protein data, imaging data) and capture nonlinear relationships between variables. Some studies have shown a slight improvement in model prediction performance between logistic regression (LR) and machine learning (ML) algorithms,(37) while others have not.(38) AI methods are showing particular promise for providing advancements in areas where disease prediction is based on complex data such as lung imaging(39) or protein data.(40) Given BLUEPRINT will test whether integration of traditional BPD risk factors with protein, imaging and other data may improve prediction of BPD outcomes, it will be important to test alternative risk prediction models. We will test several commonly used ML algorithms (e.g. K-nearest neighbour, random forests, support vector machine). LR and ML models will all be internally validated and compared using the same data. Model performance will be compared with accuracy, sensitivity and specificity.

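### The high-risk and low-risk groups in section 11.2 appear to be formed from scores fitted to the same infants' BPD status, so the displayed gap would be optimistic; use out-of-fold scores

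*Protocol*

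**What the plan says.** Protocol section 11.2 sets out the prediction work in this order.

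- **Outcome:** "We will develop a risk prediction model for BPD diagnosed at 36 weeks".
- **Inputs:** "based on a combination of proteins, imaging and clinical measures (minimum 7 inputs) derived within the first 7 days after birth".
- **Selection and fitting:** "binary logistic regression, multiple forward stepwise logistic regression, and other classification models will be evaluated with likely measures as covariates".
- **Safeguard:** "Internal validation with both cross-validation and bootstrapping methods to adjust for model over-optimism and bias towards inherent overestimated performance metrics will be applied".
- **Risk groups:** the contrast is of "differences in BPD risk outcomes between high-risk and low-risk groups based on prognostic scores derived from BPD risk models". Cox regression and Kaplan-Meier curves are the tools, and the stated purpose is to explore and display it. The sentence ends by saying that this will help to account for infants lost before 2 years.
- **Comparison of logistic and machine-learning models:** "LR and ML models will all be internally validated and compared using the same data".

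Section 11.1 expects 525 infants in the BPD modelling data set. No hold-out sample or independent cohort is named for the BPD model. The external validation in Table 3a concerns the endotypes and is done by trajectory modelling, so it does not supply new infants for the BPD score.

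**The concern.** A score chosen and fitted to separate these infants by BPD status will separate them by BPD status. Splitting the same infants at a cut-off of that score and comparing their BPD risk shows partly real prediction and partly the fit to chance.

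The safeguard does not reach this step as worded. Correcting an AUC for optimism changes the reported AUC, but it leaves each infant's fitted score, risk group and curve as they were. The risk-group sentence carries no validation wording of its own.

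At stake is a figure that readers will take as the size of the risk gap that early markers can deliver. The problem is separate from the choice of time axis: it would remain if the comparison were of two simple proportions.

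**Working it through.** **Inputs from the protocol.** BPD prevalence 0.69, C-index 0.75, and 500 / 550 / 600 infants for 10 / 11 / 12 predictors (section 11.1); 525 infants in the modelling set (section 11.1); at least 7 model inputs (section 11.2).

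**Assumed, because the protocol does not give them.** A median split of the score, a two-sided 0.05 level, and the number of candidate markers. The proteome work is described as untargeted in section 2.1, so a large pool is plausible, but no count is stated.

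**Step 1: the protocol's own sample size.** A C-index of 0.75 at prevalence 0.69 corresponds to a Cox-Snell R² of 0.162 (by simulation). With a target shrinkage of S = 0.9 (assumed), the governing criterion is n = p / [(S − 1) ln(1 − R²/S)].

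- For p = 10: 10 / [−0.1 × ln(1 − 0.162/0.9)], about 506.
- For p = 11 and 12: 556 and 607.

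These agree with 500 / 550 / 600 to within 3%. For the loss allowance, 550 × 0.95 = 522.5, against 525 stated. The inputs are therefore usable as they stand.

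**Step 2: noise markers, fixed terms.** With 525 infants, 69% BPD and independent noise predictors, a logistic model was fitted, the infants were split at the median fitted score, and BPD was compared between halves (1,000 runs each).

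| Terms | BPD high | BPD low | Gap (points) | p<0.05 if tested |
|---|---|---|---|---|
| 7 | 73.1% | 64.8% | 8.3 | 56% |
| 10 | 74.1% | 64.0% | 10.1 | 74% |
| 12 | 74.4% | 63.5% | 10.9 | 82% |

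A second simulation gave 8-11 points and p<0.05 in 52-84% of studies.

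**Step 3: noise markers, with selection.** Forward stepwise entry at p<0.05, at most 12 terms (300, 150 and 60 runs):

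| Candidates | BPD high | BPD low | Gap (points) | p<0.05 if tested | Apparent AUC |
|---|---|---|---|---|---|
| 30 | 73.1% | 64.9% | 8.2 | 58% | 0.57 |
| 100 | 77.4% | 60.7% | 16.7 | 99% | 0.64 |
| 300 | 83.0% | 55.1% | 27.9 | 100% | 0.73 |

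When exactly 10 terms are picked from 100-300 candidates, the gap is 21-25 points and p<0.05 occurs in every run. The two selection rules differ, so their gaps do too.

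**Step 4: real signal.** At a true C of about 0.75 with pre-fixed terms, the apparent gap against the gap in new infants is about 32 vs 30 points (7 terms), 32 vs 29-30 (10) and 32 vs 29 (12). Across simulations the overstatement is about 2-4 points. With selection from 50-300 candidates it is about 7-11 points.

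**Step 5: does the remedy work?** Out-of-fold groups with cut-offs set in the training folds average a gap of about 0 under the null and match new infants when there is signal. Naive tests need care. On pooled out-of-fold scores split at one overall median, p<0.05 occurred in 4-9% of null runs in the expected direction but in 14-20% counting both directions. On new infants it occurred in about 5-9%.

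**The case against.** The strongest reply has four parts.

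1. **In-sample scoring is not stated.** The text does not say whether the scores are apparent or out-of-fold, cross-validation is planned in the same section, and a separate SAP may settle the matter. This stands in part: in-sample use is the natural reading, not an explicit one. But the protocol itself names the groups, the score and the methods, and it ties validation to performance metrics. That makes it a stated analysis that needs correcting, not merely a detail left open.

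2. **No significance test is planned.** The purpose is to investigate and illustrate, with no level or decision rule. This stands, and the rejection rates above apply only if someone tests. The gap itself is optimistic with or without a test.

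3. **The outcome may not be BPD at 36 weeks.** The clause on loss before 2 years suggests later outcomes, and a BPD-trained score compared on later respiratory health is not direct resubstitution. The ambiguity is real, although the sentence itself says BPD risk outcomes.

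4. **The null case is not the protocol's case.** Section 2.1 lists factors known to be associated with BPD, and section 11.1 expects a C-index of 0.75 and sizes the study to limit overfitting. At that C with fixed terms the optimism is small. This stands and sets the lower end of the size given here.

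A reader might infer that the groups are bound to differ significantly even if no marker predicts anything. The documents do not support that. With 7-12 fixed noise terms a significant result is likely but not certain, and near-certainty needs selection from a pool of about 100 or more, a count the protocol does not give. Nor do they support calling this the main clinician-facing result: the prediction tool is that, and it is judged by AUC, accuracy, sensitivity and specificity.

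**Conclusion.** The concern holds in a limited form. Section 11.2 does not extend its validation to the risk groups, and if fitted scores form them, the displayed gap in BPD risk is too large. At the protocol's expected C-index of about 0.75, the overstatement is about 2-4 points with 7-12 fixed terms and about 7-11 points with selection from 50-300 candidates. With pure-noise markers the whole apparent gap is artefact: about 8-11 points with fixed terms and about 21-25 points when 10 terms are picked from 100-300 candidates.

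These sizes rest on the assumed median split and candidate counts, and on the reading that apparent scores are used. The comparison supplements the prediction aim and does not touch the primary endotyping objective, so the severity is modest.

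**What to change.** In section 11.2, or in the SAP with a reference from it:

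- Assign each infant to a risk group from a cross-validated (out-of-fold) score. Repeat the full selection and fitting in each training fold, and set the cut-off in advance or within the training folds.
- Report observed BPD risk per group from that assignment.
- Give no p-value or hazard ratio for groups formed from in-sample scores.
- Obtain any p-value or interval for the out-of-fold groups by permuting or bootstrapping the whole pipeline, since naive tests on pooled out-of-fold scores are not exactly calibrated.
- State whether the curves show BPD at 36 weeks or a later respiratory outcome.

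Cross-validation is already planned, so the cost is a few sentences and a little more analysis work. The reported gap will be smaller.

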Defining the early origins of BPD progression is essential to improving outcomes

Reducing the rate of BPD continues to challenge neonatologists, with few therapies demonstrating benefit to date.(2, 9) BPD results from injury initiated in the early neonatal period and is exacerbated by other morbidities such as sepsis. Currently, BPD is diagnosed at 36 weeks' PMA,(2, 10-12) well after the initiating events. This late diagnosis limits the application of interventions designed to alter respiratory outcomes.(9) Several clinical factors (e.g. gestation, sex, chorioamnionitis, duration of mechanical ventilation and supplemental oxygen needs) are associated with BPD.(2) However, none alone or in combination have shown to accurately predict the risk.(9, 11) The reasons for this inaccuracy may lie in the use of measures that are too crude to allow prediction of this complex disease. This is perpetuated by a 'one-size-fits-all' approach to applying various respiratory therapies available in the NICU (e.g. continuous positive applied pressure, high-flow nasal cannula, intubation).(2) Therefore, to progress and reliably predict respiratory risks, there is a pressing need to identify these complex early phenotypes at a biological systems level. Such information will not only serve as targets for interventions aimed at ameliorating lung injury, but to also guide respiratory decisions in the crucial period shortly after birth when strategies to prevent BPD may have the most benefit.

BPD is the result of a multi-modal inflammatory cascade of events but is defined purely on clinical status. Our pilot work suggests that the inclusion of both protein and lung function (imaging) measures (with clinical data) in the first 7 days can differentiate respiratory phenotypes that improve the accuracy of BPD prediction. This is the critical first step in implementing stratified lung protective respiratory care based on evidence before the initial injury-inflammation cascade becomes entrenched.

Defining the landscape of early preterm life: many phenotypes, many choices, many outcomes

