3.1.3 Exploratory objectives

The BLUEPRINT study aims to explore the role of precision medicine and prediction modelling in neonatal critical care, and the development of new approaches to understanding long-term respiratory impacts of preterm birth that may address some of the limitations of the use of BPD and the lack of sound methods of defining respiratory health in infancy.

There are some important exploratory objectives that may arise from this study. Specifically:

1. Whether respiratory health and complications of preterm birth can be better defined using an alternative set of diagnostic criteria for BPD that better reflect functional respiratory health and clinical events in the NICU, or a new entity entirely based upon new biomarkers.
2. Whether plasma protein biomarkers can improve the ability to define respiratory trajectory following preterm birth, specifically with relation to response to respiratory care and early identification of complications of preterm birth.

3. Whether LUS and EIT biomarkers can improve the ability to define respiratory trajectory following preterm birth, specifically with relation to type of respiratory care and complications of NICU and preterm birth.
4. Whether heterogeneity of ventilation is a predictor of later BPD and respiratory health at 1 and 2 years (corrected).
5. Whether a series of measures or definition of respiratory health at 1 and 2 years can be developed that would provide a more meaningful representation of the respiratory impact of preterm birth than the diagnosis of BPD.
6. Whether the inclusion of unsupervised plasma proteomics and LUS and EIT may identify novel treatments via identification of previously unexplored concepts and/or molecules that influence preterm respiratory outcomes.
7. Whether the comprehensive clinical, imaging and protein datasets generated may allow for a better understanding of the extrapulmonary impact of preterm respiratory disease.
8. To determine the relationship between maternal and fetal characteristics and plasma protein abundance at 72 hours and 7 days post-birth.

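### The protocol says it will test whether protein and imaging data improve BPD prediction over traditional risk factors, but specifies no comparison that isolates what those data add

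*Protocol*

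**What the plan says.** Section 11.2, under the part on alternative machine learning models, gives as the reason for trying them: "Given BLUEPRINT will test whether integration of traditional BPD risk factors with protein, imaging and other data may improve prediction of BPD outcomes". It then fixes the comparison: "LR and ML models will all be internally validated and compared using the same data. Model performance will be compared with accuracy, sensitivity and specificity".

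The preceding part of Section 11.2, on the BPD risk model, describes a model "based on a combination of proteins, imaging and clinical measures (minimum 7 inputs) derived within the first 7 days after birth". It plans variable selection (including forward stepwise logistic regression), an assessment of performance and discrimination, and internal validation by cross-validation and bootstrapping.

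The idea of improvement also appears elsewhere. The background in Section 2.1 reports pilot work suggesting that protein and imaging measures, used with clinical data, "can differentiate respiratory phenotypes that improve the accuracy of BPD prediction". Exploratory objective 2 in Section 3.1.3 asks "Whether plasma protein biomarkers can improve the ability to define respiratory trajectory following preterm birth", and objective 3 asks the same of lung ultrasound (LUS) and electrical impedance tomography (EIT).

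Section 11.1 sizes the study for developing one binary logistic model with prevalence 0.69 and C-index 0.75. It gives 500, 550 or 600 infants for 10, 11 or 12 predictors, and expects 525 infants in the BPD modelling set. Section 11.2 refers to a separate SAP, which was not available for this review.

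**The concern.** To say that a set of inputs improves prediction, one must compare performance with and without them, in the same infants and with the same modelling procedure. Section 11.2 names a combined model and a comparison of algorithms. Neither part mentions a model restricted to traditional or clinical factors, or a measure of the gain over one.

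At stake is what the combined model's performance can be taken to mean. A C-index near 0.75 would include whatever gestation, sex and early respiratory support achieve alone. Without a clinical-only benchmark, the study could not say whether blood sampling, mass spectrometry, LUS and EIT improve BPD prediction beyond information every unit already holds.

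**Working it through.** **1. Does any stated analysis supply the contrast?**

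| Stated analysis | Where | What it varies | Shows what biomarkers add for BPD? |
|---|---|---|---|
| Combined BPD model | 11.2 | Nothing; one mixed pool of candidates | No |
| Forward stepwise selection | 11.2 | Which measures enter the mixed model | No; it tests entry and does not estimate performance gained |
| Logistic regression vs machine learning | 11.2 | The algorithm | No |
| Endotypes vs BPD diagnosis (secondary objective 8) | 3.1.2, Table 3a | The predictor, but for 1- and 2-year outcomes | No |
| Accuracy of the LUS score for BPD | Table 3a | LUS score assessed for BPD, with no contrast against clinical factors | No |

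**2. Does the sample size cover it?** Inputs from Section 11.1: prevalence 0.69 and C-index 0.75. By simulation these correspond to a Cox-Snell R² of 0.1618. The driving criterion, with shrinkage S = 0.9 (assumed), is

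n = p / [(S − 1) ln(1 − R²/S)]

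Here ln(1 − 0.1618/0.9) = −0.198, so the denominator is 0.0198. For p = 10, 11 and 12 this gives 505, 556 and 606, against 500, 550 and 600 stated. The plan's figures are reproduced to within about 1%. They concern the development of one model and hold no term for a difference between two models.

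**3. How informative is accuracy at this prevalence?** Labelling every infant BPD gives accuracy 0.69, sensitivity 1 and specificity 0. For a binormal score, d = √2 Φ⁻¹(C), the accuracy-maximising cut-off is t = d/2 − ln(0.69/0.31)/d, and

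accuracy = 0.69 Φ(d − t) + 0.31 Φ(t)

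At C = 0.75, d = 0.954 and t = −0.362. Sensitivity is then 0.906 and specificity 0.359, so accuracy = 0.69 × 0.906 + 0.31 × 0.359 = 0.736.

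| C-index | Best accuracy |
|---|---|
| Call all BPD | 69.0% |
| 0.65 | 69.8% |
| 0.70 | 71.3% |
| 0.73 | 72.6% |
| 0.75 | 73.6% |

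Only 0.75 is a plan figure; the other C-indices are assumed clinical-only values. The whole range spans less than 5 percentage points above the no-information rule.

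**4. Could the planned cohort estimate the gain?** 525 × 0.69 ≈ 362 infants with BPD and 163 without. Assume a clinical score with C = 0.65, 0.70 or 0.73, plus an independent biomarker score that brings the combined C to 0.75. Simulating 2,000 datasets gives:

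| Clinical-only C (assumed) | Gain in C | SE of paired difference | Gain ± 1.96 SE |
|---|---|---|---|
| 0.65 | 0.10 | 0.023 | 0.055 to 0.145 |
| 0.70 | 0.05 | 0.017 | 0.017 to 0.083 |
| 0.73 | 0.02 | 0.011 | −0.002 to 0.042 |

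These SEs exclude model-fitting uncertainty. As a cross-check, Hanley-McNeil standard errors with a correlation of 0.5 to 0.7 between the two C-indices give power of 61% to 82% when the clinical-only C is 0.70, and 15% to 22% when it is 0.73 (two-sided 5%).

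**The case against.** The strongest reply is that a protocol need not list every nested model. Section 11.2 defers to a separate SAP, all data domains come from the same cohort, and the comparison stays available at analysis. That stands as far as it goes. A reader might infer that the added value will never be measured, but with the SAP unseen the protocol cannot show that. What remains is more than missing detail: the protocol announces a test and specifies a comparison that would not carry it out.

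A second reply concerns the quoted sentence. It is a subordinate clause explaining why machine learning is worth trying. A reader might infer that the algorithm comparison is the plan's answer to the added-value question; the text does not say so. Nor does "LR and ML models will all be internally validated and compared using the same data" necessarily mean identical inputs, since it may only mean the same dataset. Either way, no contrast with and without biomarkers is stated.

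Third, no primary or secondary objective is worded as incremental value for BPD. The exploratory objectives concern respiratory trajectory, and the background sentence reports pilot work. This is fair and limits the weight of those passages. The explicit statement in Section 11.2 carries the point.

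Fourth, accuracy, sensitivity and specificity are named for the algorithm comparison. Discrimination is planned for the BPD model, and specificity of 0 would expose the call-all-BPD rule. This also stands: the metrics are a secondary weakness, not the core.

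Finally, a reader might subtract the assumed gains (0.02 to 0.10) from the 0.25 by which a C-index of 0.75 exceeds chance, and conclude that the biomarkers' value would be overstated by 15 to 23 points. The documents do not support that. The clinical-only C-index is not given, and nowhere does the protocol credit all discrimination above chance to the biomarkers.

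**Conclusion.** The point holds as a mismatch between a stated test and the stated comparison. For BPD, the protocol names one combined-input model and one comparison, of algorithms. Neither isolates what protein and imaging data add, and the nearby analyses do not fill the gap. This is a statement about the protocol as written, not about what the SAP may contain.

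No single figure measures the consequence, because the clinical-only C-index is unknown. Two sizes are informative. On accuracy, the plan's own target of C = 0.75 reaches at most about 73.6% against a floor of 69%, assuming binormal scores. On the C-index, 525 infants give a standard error for the paired difference of roughly 0.01 to 0.02, assuming a clinical-only C-index of 0.65 to 0.73 and independent biomarker information. Gains of 0.05 or more could be estimated usefully. A gain of about 0.02 may not be distinguishable from zero, and correlation between biomarkers and gestation or treatment would change these values. The change is worth making now because it is cheap and fixes the comparison before results are seen.

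**What to change.** In Section 11.2, or in the SAP with a reference from 11.2:

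- Pre-specify a clinical-only reference model for BPD from first-week variables already collected, for example gestational age, birth weight, sex and respiratory support.
- Fit clinical + imaging, clinical + protein, and clinical + imaging + protein models in the same infants, with the same algorithm and the same cross-validation or bootstrap procedure, repeating any variable selection within each resample.
- Make the optimism-corrected paired difference in C-index against the clinical-only model, with a bootstrap confidence interval, the test of added value.
- Keep logistic regression versus machine learning as a secondary comparison of algorithms, and report any accuracy beside the 69% no-information value.

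The cost is a few paragraphs and some extra model fits. No further infants, samples or visits are needed. The downsides are that the headline benefit of the biomarkers may look smaller than the combined-model C-index suggests, and that a small gain will be estimated with limited precision, which the plan should acknowledge.
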